| ICD | implantable cardioverter defibrillator |
| ICH | International Council on Harmonization |
| ICU | Intensive Care unit |
| IfU | Instructions for Use |
| ITT | Intent To Treat |
| ISF | investigator site file |
| KKS | Coordination Centre for Clinical Trials |
| LPLV | last patient last visit |
| MPG | german medical device law |
| MRI | magnetic resonance imaging |
| NA | not applicable |
| NaCl | Sodium chloride |
| ND | not done |
| OLV | one lung ventilation |
| PDA | peridural anesthesia |
| PEEP | positive end-expiratory pressure |
| SAE | serious adverse event |
| SADE | serious adverse device effect |
| SAS | statistical analysis system |
| SBT | spontaneous breathing trial |
| SDV | source data verification |
| SOP | standard operating procedure |
| SPSS | statistical package for the social sciences |
| TEA | thoracic epidural anesthesia |
| TMF | trial master file |
| USADE | unanticipated serious adverse device effect |
| VT | tidal volume |

1.2 SYNOPSIS

| | |
|--------------------------------|--|
| Title | Assessment of the capability of PulmoVista 500 to continuously monitor changes of ventilation over time. |
| Short Title | PulmoVista 500 |
| Target population | 
Following patients will be enrolled:
 
 - Intensive care unit (ICU) patients, who are mechanically ventilated via an artificial airway (endotracheal tube or tracheostomy cannula) and who are expected to be subjected to major changes in their ventilator settings will be monitored with the PV500 device before, during and after the changes. These changes in the ventilator settings should result in recognizable changes in the distribution of ventilation in the lungs. 
Examples of such interventions are:
 
 • Spontaneous breathing trial (SBT) using the ventilator (as opposed to SBT using a T-piece) • Switching between different modes of ventilation (e.g. volume controlled, pressure controlled, pressure support, CPAP) • Initial adjustment of ventilation after ICU admission • Weaning from ventilation in preparation for extubation • PEEP trials and recruitment maneuvers • Suctioning maneuvers - Patients who are scheduled for surgeries that require blocking of one bronchus (e.g. one-lung-ventilation by insertion of a double lumen tube or bronchial blocker) |
| Trial design | Multicenter, prospective, non-interventional, open trial |
| Objectives of the Trial | 
Primary objective
 
The capability of PulmoVista 500 to continuously
 |

| | |
|--------------------------------------|---|
| | 
monitor ventilation and its changes.
 
Secondary Objective
 
 • To assess the capability of PulmoVista 500 to detect regional changes of ventilation and lung volume. • Documentation of any safety events related to the use of PulmoVista 500 • Assessing the use specific clinical helpfulness of PulmoVista 500 |
| 
Endpoints of the Trial
 | 
Primary Endpoint
 
The capability of PulmoVista 500 for continuous monitoring of ventilation and its changes at different points in time during varying states of regional ventilation, the cross-correlation function (CCF) between global tidal impedance (EIT) waveforms and global tidal volume (ventilator) curves will be evaluated.
 
Secondary Endpoints
 
 - First secondary endpoint: To assess the capability of PulmoVista 500 to detect changes in regional ventilation by evaluating the cross correlation between impedance waveforms derived from PulmoVista 500 and volume curves derived from ventilator during one-lung-ventilation. - Assess that changes of tidal volumes induced by ventilator settings can be monitored by the "Trends view" (see chapter 23.2) - Assess that changes of the end-expiratory lung volumes (induced by e.g. PEEP changes, recruitment and suctioning maneuvers) can be monitored by "dEELI trend view" (see chapter 23.2) - Documentation of any safety events related to the use of PulmoVista 500 - Clinical helpfulness of PulmoVista 500 is proven if 
 • see attachments (chapter 23.1) clinical usability |
| 
Sample Size
 | 
 • 80 patients 
25 patients shall be enrolled in a subgroup of patients with one-lung-ventilation (OLV)
 |

| | |
|-----------------------------|--|
| Anticipated Duration | 
Relating to trial
 
First patient first visit: January 2017
 
Last patient last visit: September 2017
 
Relating to patient: 8 hours (+Safety Follow-up)
 |
| Inclusion Criteria | 
 The population included in the clinical study will be selected from a pool of patients undergoing respiratory support who are scheduled to have their ventilation settings changed. As a subgroup, patients who are scheduled for surgeries that need one-lung-ventilation (OLV) will be enrolled to the study. Male and female patients at the age of 18 years or older On respiratory support in ICU care or scheduled for such (e.g. postoperatively) or scheduled for surgery with OLV Patients of which the monitoring of ventilation distribution may be of clinical interest Patients being ventilated via an artificial airway with a mechanical ventilator that is compatible with PulmoVista 500 Patients scheduled for changes in ventilation settings that may cause relevant changes in the ventilation Chest circumference between 70 and 150 cm Written informed consent to participate in the study provided by either the patient or the legal representative of the patient. |
| Exclusion Criteria | 
 Currently has a permanent or temporary pacemaker, implantable cardiac device (ICD) or other device emitting electrical energy a BMI ≥ 50 tidal volume (VT) ≤ 200 mL Current uncontrolled body movements such as tics, tremors or seizures, Current wound dressings or infections on the chest that might interfere with the PulmoVista 500 electrode belt placement Women of child bearing potential whose pregnancy cannot be excluded based on a pregnancy test or other proven facts. |

| | |
|---|--|
| | 
 • Allergic to materials used in the electrode belt • Participation of the patient in an interventional trial within the last four weeks before enrollment in this trial • Evidence suggesting that the patient or his legal representative is not likely to follow the trial protocol (e.g. lacking compliance) • Known infectious diseases that require isolation of patient (e.g. MRSA) • Concomitant use of an air anti-decubitus medical mattress with dynamic inflation that cannot be deactivated during EIT measurements |
| Conduct of the trial | 
Visit 1 - Screening and Enrollment (Day (-2) - 0))
 
 • Screening • Pregnancy Test or Exclusion • Check Inclusion and Exclusion Criteria • Informed Consent Process • Demography • Clinical Anamnesis • Medical History 
Visit 2 (Day 0)
 
 • EIT measure • Recording of EIT Data 
Visit 3 - Follow up (Day 1 - 3)
 
 • Check of adverse events 
General
 
 • Data of CT-, MRI-images, ultrasound assessments and radiographs not taken especially for this study, but due to necessary medical treatment taken during the period of day -2 to +3. |
| Trial related procedures and laboratory examinations | 
 • Measurement with PulmoVista 500 during ventilation for a maximum period of eight hours • Pregnancy test if necessary |
| Investigational device | PulmoVista 500 is a non-invasive monitoring device used as an adjunctive diagnostic tool for assessing the distribution of ventilation in |

| | |
|----------------------|---|
| Manufacturer: | patients undergoing respiratory support. Drägerwerk AG & Co. KGaA [name] [name], Germany |
|----------------------|---|

Table 1: Visit Schedule

| scheduled for day | Visit 1 Screening and Enrollment (-2) or (-1) or 0 | Visit 2 Trial 0 | Visit 3 Follow Up (safety) 1 or 2 or 3 |
|------------------------------|---|--------------------------------------|---|
| Informed Consent | x | | |
| Inclusion/Exclusion Criteria | x | | |
| Demographics | x | | |
| Medical/Treatment History | x | | |
| Vital Signs | x | x | |
| Pregnancy Testing | x | | |
| SAE administration | | x | x |

2 INVESTIGATIONAL DEVICE PULMOVISTA 500

2.1 SUMMARY DESCRIPTION AND PURPOSE

PulmoVista 500 is a lung function monitor for clinical use which continuously generates cross-sectional images of the lung function by applying the technique of electrical impedance tomography (EIT).

To perform bio-impedance measurements, an electrode belt containing 16 electrodes is placed around the chest wall. Additionally, one reference electrode must be attached to a central point to the body, preferably on the abdomen. The reference electrode ensures that all measurements at different electrode pairs are referenced to the same electric potential¹.

PulmoVista 500 provides graphical information about the regional distribution of ventilation and changes of end-expiratory lung volume. The temporal resolution of this information allows observing specific conditions of different lung regions.

PulmoVista 500 is a CE released class IIa medical device manufactured by Drägerwerk AG & Co. KGaA, Lübeck Germany. It is distributed within Europe since April 2011.

2.2 DETAILS CONCERNING THE MANUFACTURER

Drägerwerk AG & Co. KGaA is an international company in the fields of medical and safety technology. Since 1889, Dräger has been developing technical devices and solutions for use in clinical, industrial or mining applications, in firefighting or rescue services.

2.3 MANUFACTURING OF PULMOVISTA 500 AND SUPPLY TO THE TRIAL SITES

The device PulmoVista 500 is produced by the Drägerwerk AG & Co. KGaA Dräger provides one of the devices to each trial site as a loan device for the duration of the study.

2.4 DESCRIPTION OF THE INVESTIGATIONAL DEVICE

[figure not shown]
PulmoVista 500 is a non-invasive monitoring device used as an adjunctive diagnostic tool for assessing the distribution of ventilation. PulmoVista 500

¹ Teschner E, Imhoff M, Leonhardt S. Electrical Impedance Tomography: The realisation of regional ventilation monitoring. Drägerwerk AG & Co. KGaA 2015; Reference-Nbr 90 66 788; 19

allows visualization and evaluation of the lungs by applying the Electrical Impedance Tomography (EIT) technique.

PulmoVista 500 continuously determines the regional bioimpedance of the tissue within one cross-sectional plane (the so-called "electrode plane") of the thorax. To perform the EIT measurements, an electrode belt (F) containing 16 electrodes has to be placed around the chest wall of the patient and must be connected to PulmoVista 500 via a patient cable and a trunk cable (G, H). The electrode belt is made of silicone rubber, whereas the electrodes are made of conductive, carbonized silicone rubber. The electrode cables are made of different plastics (thermoplastic polyurethane (TPU), polyamide (PA), polyurethane (PUR), polypropylene (PP), thermoplastic elastomer (TPE), polybutylene terephthalate (PBT)). The impedance of lung tissue varies with the air content. Thus, ventilation distribution and changes of end-expiratory lung volume that occur within the electrode plane can be detected and displayed.

PulmoVista 500 is made up of the Infinity Medical Cockpit C500 (A), the Power Supply Unit P2500 (E) and the EIT module (C). Handle (B) and trolley (D) allow easy transport of PulmoVista 500 within the hospital.

Infinity Medical Cockpit C500 (A)

The Infinity Medical Cockpit provides the user interface of PulmoVista 500 in form of a standardized display and control unit that is also used in other Dräger products. The display software running on the Infinity Medical Cockpit

uses common standardized operating concepts applied for various Dräger products to facilitate ease of use for the clinicians.

Power Supply Unit P2500 (E)

The Power Supply Unit P2500 converts the AC mains supply voltage into a DC safety low voltage to power the EIT module as well as the Infinity Medical Cockpit. The Power Supply Unit is medical grade implementing all required safety measures for medical electrical equipment to protect patient, user and bystander.

EIT Module (C)

The EIT module is the signal processing front-end that generates the measurement currents and determines the resulting voltages at the chest electrodes.

The software version of PulmoVista 500 is named as 1.12. Upgrades of this version will be possible and documented

| Applied Standards in full or in part: | |
|--|--|
| EN ISO 14971: 2009 (ISO 14971: 2007) | Medical Devices - Application of Risk Management to Medical Devices |
| EN 60601-1: 2006 / AC: 2010 (IEC 60601-1: 2005 / CORR 1: 2006 / CORR 2: 2007) (IEC 60601-1:1988/A1: 1991/A2: 1995) | Medical electrical equipment -- Part 1: General requirements for basic safety and essential performance |
| EN 60601-1-2: 2007 / AC: 2010 (IEC 60601-1-2: 2007) (IEC 60601-1-2:2001/A1:2004) | Medical electrical equipment Part 1-2: General requirements for safety – Collateral standard: Electromagnetic Compatibility - Requirements and tests |
| EN 60601-1-6: 2007 (IEC 60601-1-6: 2006) (IEC 60601-1-6: 2004) | Medical electrical equipment Part 1-2: General requirements for safety – Collateral standard: Usability |
| EN ISO 10993-1: 2009 / AC : 2010 (ISO 10993-1: 2009) | Biological Evaluation of Medical Devices – Part 1: Evaluation and Testing within a Risk Management Process |
| EN ISO 10993-5: 2009 (ISO 10993-5: 2009) | Biological Evaluation of Medical Devices – Part 5: Tests for in Vitro Cytotoxicity |
| EN ISO 10993-10: 2009 (ISO 10993-10: 2009) | Biological Evaluation of Medical Devices – Part 10: Tests for Irritation and Delayed-Type Hypersensitivity |
| EN 980: 2008 | Graphical symbols for use in the labelling of medical devices |
| EN 1041: 2008 | Information supplied by the manufacturer with medical devices |

2.5 Summary of the necessary training and experience needed to use PULMOVISTA 500

During the initiation visit of each trial site a training has to be performed by a representative of Drägerwerk AG & Co. KGaA introducing the use of the device and standardized data acquisition for study purposes.

3 JUSTIFICATION FOR THE DESIGN OF THE CLINICAL TRIAL

3.1 BACKGROUND

Acute Lung Injury (ALI) is a very common complication within the population of intensive care patients^{2 3 4}. It has been shown that mechanical ventilation with ventilator settings which do not suit the individual requirements of the diseased lung can lead to injury of the cellular structures of the lung tissue. As a result, vascular and alveolar permeability increases and interstitial edema formation occurs. Due to the increased weight of the lung, alveolar collapse may predominantly occur in the independent lung regions, resulting in even more severe hypoxemia^{5 6}.

4 RISKS AND BENEFITS OF THE INVESTIGATIONAL DEVICE AND CLINICAL INVESTIGATION

4.1 ANTICIPATED CLINICAL BENEFIT AND ANTICIPATED ADVERSE DEVICE EFFECTS

Anticipated clinical benefit:

By participating in the clinical study, the patient benefits of a close monitoring as part of the study, which goes beyond the clinical routine.

Anticipated adverse device effects:

The use of the device according to the normal conditions of use, may cause skin irritation to the patient or pressure marks caused by the electrode belt.

4.2 RESIDUAL RISKS ASSOCIATED WITH THE INVESTIGATIONAL DEVICE, AS IDENTIFIED IN THE RISK ANALYSIS REPORT

Residual Risk associated with the Investigation Device:

PulmoVista 500 is a CE released class IIa medical device. According to the risk analysis for the conformity assessment according to the ISO 14971 there exists no unacceptable individual or overall residual risk for the medical device.

Risks associated with participating in the clinical trial:

Since the study is a non-interventional observational study without additional study-related changes in the treatment of patients, no additional study risks occur through the participation in this clinical study.

4.3 POSSIBLE MUTUAL REACTIONS

The use of the device according to the normal conditions of use, may cause skin irritation to the patient or pressure marks caused by the electrode belt.

(see above 4.1)

4.4 PROCEDURE TO REDUCE RISKS

As described in the instructions for use of the device the patient's skin should be checked periodically for any discomfort or injury.

In case of intolerance reactions, signs of progressive infection, skin reactions or mechanical irritation, which go beyond the usual extent, the measurement is interrupted and an adequate therapy initiated. The patient will be requested to report problems immediately to the investigator.

5 OBJECTIVES AND HYPOTHESES

5.1 OBJECTIVES

5.1.1 PRIMARY STUDY OBJECTIVES

To assess the capability of PulmoVista 500 to continuously monitor ventilation and its changes.

5.1.2 SECONDARY STUDY OBJECTIVES

- To assess the capability of PulmoVista 500 to detect regional changes of ventilation and lung volume.
- Documentation of any safety events related to the use of PulmoVista 500
- Assessing the use specific clinical helpfulness of PulmoVista 500

6 DESIGN OF THE CLINICAL INVESTIGATION

6.1 GENERAL

The clinical trial will be conducted according to the German Medical Device Act as § 23 b clinical trial. There is no need to access an approval by federal authority (BfArM).

The trial can start only after obtaining a positive review by all local Ethics Committees. The written approval of the EC and written exemption of approval must be filed in the Sponsor File. Additionally, every participating site must receive a copy of these documents to be filed in the Investigator Site File (ISF).

6.1.1 TYPE, DESIGN, PRINCIPAL INVESTIGATOR

The trial is a multicenter observational study. This study will be conducted in compliance with ISO 14155. It is sponsored by Drägerwerk AG. Drägerwerk AG assumes all responsibilities as the sponsor of this study.

Coordinating Investigator: PD Dr. med. [name]
Universitätsklinikum Carl Gustav Carus
Dresden

Medical Advisor: Associate Professor (USA)
Dr. med. [name]
Klinik für Anästhesiologie
und Operative Intensivmedizin
Klinikum Bremerhaven-Reinkenheide gGmbH

6.1.2 BLINDING

This is an observational trial of intraindividual correlation between two methods of measurement. Since we do not allocate patients to treatment and placebo groups as it would be the case in a randomized trial, blinding is not strictly necessary. However, patients will be blinded to the results of the investigational EIT device by either a) being sedated in the ICU or under general anesthesia or b) device will not be facing them so they cannot see the results.

Study personnel at bedside will not be blinded as they have to interact with the device (to ensure quality of data recording) and therefore blinding is not feasible.

The medical personal responsible for the patient's medical care does not use the information given by the PulmoVista 500 .

6.1.3 PRIMARY AND SECONDARY STUDY ENDPOINTS

PRIMARY STUDY ENDPOINT

The capability of PulmoVista 500 for continuous monitoring of ventilation and its changes at different points in time during varying states of regional ventilation, the cross-correlation function (CCF) between global tidal impedance (EIT) waveforms and global tidal volume (ventilator) curves will be evaluated.

SECONDARY STUDY ENDPOINTS

- First secondary endpoint: To assess the capability of PulmoVista 500 to detect changes in regional ventilation by evaluating the cross correlation between impedance waveforms derived from PulmoVista 500 and volume curves derived from ventilator during one-lung-ventilation.
- Assess that changes of tidal volumes induced by ventilator settings can be monitored by the "Trends view"
- Assess that changes of the end-expiratory lung volumes (induced by e.g. PEEP changes, recruitment and suctioning maneuvers) can be monitored by "dELLI trend view"

- Documentation of any safety events related to the use of PulmoVista 500
- Assessing the use specific clinical helpfulness of PulmoVista 500 - clinical helpfulness of PulmoVista 500 is proven if
 - see attachments (chapter 23.1) clinical usability

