7 STATISTICAL CONSIDERATIONS

7.1 SAMPLE SIZE, DROP-OUT-RATES, LEVEL OF SIGNIFICANCE AND POWER OF THE CLINICAL INVESTIGATION

Primary Endpoint (Efficacy)

Based on former porcine trials⁷ with PulmoVista 500 and data from clinical studies with other EIT devices the sample size was calculated using the program G*Power 3.1.9.2.

An α -error of $p = 0.05$ and a power = 0.9 in a two-sided testing resulted in a sample size of 68 patients. With this sample size a difference of 0.1 of the mean cross-correlation coefficient shall be detected, i.e. the true value of a calculated mean of 0.8 will not be smaller than 0.7 and not be larger than 0.9 with the given p-value and power under the assumption of a standard deviation of less than .25.

Accounting for 15 % potential drop-outs 80 patients shall be enrolled in the study.

Secondary Endpoint (Efficacy)

Based on former porcine trials with PulmoVista 500 and data from clinical studies with other EIT devices the sample size was calculated using the program G*Power 3.1.9.2. An α -error of $p = 0.05$ and a power = 0.9 in a two-sided testing resulted in a sample size of 22 patients. With this sample size a difference of 0.1 of the proportion between reference and investigated variable shall be detected.

Accounting for 15 % potential drop-outs 25 patients shall be enrolled in this subgroup of the study.

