7.2 STATISTICAL DESIGN

Null-Hypothesis

The PulmoVista 500 is not capable of continuously monitoring ventilation.

Primary Endpoint (Efficacy)

To assess the capability of PulmoVista 500 for continuous monitoring of ventilation and its changes at different points in time during varying states of regional ventilation, the cross-correlation function (CCF) between global tidal impedance (EIT) waveforms and global tidal volume (ventilator) curves will be evaluated.

- To refute the null-hypothesis of this trial it must be shown that the global tidal impedance waveforms and the global tidal volume curves correlate

⁷ Fischer E, Gremse F. Assessment of the capability of PulmoVista® 500 to continuously monitor regional ventilation distribution and its changes over time. An Animal Study. FINAL STUDY REPORT. PulmoVista 500-30022. Aix Scientifics. 2016-01-27

significantly, i.e. that the correlation scores are significantly different from zero.

- If the null-hypothesis is refuted the capability of PulmoVista 500 is assumed to be a valuable diagnostic device for long-term monitoring of mechanical ventilation.

The mean value of the intra-subject cross-correlation function (CCF) between global impedance (EIT) waveforms and global volume (ventilator) curves will be determined.

Secondary Endpoint (Efficacy)

To assess the capability of PulmoVista 500 to detect regional changes of ventilation it shall be tested, whether EIT can correctly differentiate between normal and single-lung ventilation.

- To refute the null-hypothesis of this trial it must be shown that the regional information about tidal impedance variation matches the clinical changes from normal to single-lung ventilation, i.e. that EIT detects ventilation vs. no ventilation in each lung.
- If the null-hypothesis is refuted the capability of PulmoVista 500 is assumed to be a valuable diagnostic device for detecting regional ventilation changes during long-term monitoring of mechanical ventilation.

The diagnostic output of the EIT measurements will be compared with clinical ventilation settings in a 2x2 table.

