To refute the hypothesis of independence of both waveforms, it has to be shown that the global impedance waveforms (as measured by the PulmoVista 500) and the global volume waveforms (of the EvitaV500 ventilator) correlate significantly (rejection of the null hypothesis "no correlation"). Because 2 experimental steps (before and after each intervention) should be performed in 80 patients, 80 averaged (from the pre- and post-values) cross-correlation coefficients will be obtained in total. If, for technical reasons (for example, incorrectly set markers), there are only pre- or post-values, the averaging in this patient is omitted and only one cross-correlation coefficient is used. From these averaged cross-correlation coefficients, a 95% confidence interval is calculated and a one sample t-test is performed to determine if the mean of the cross-correlation coefficients is significantly different from zero.

The significance level is $\alpha = 0.05$.

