5.6 SECUNDARY ANALYSIS

5.6.1 Efficacy

- To demonstrate the ability of PulmoVista 500 to visualize regional ventilation changes, a quantitative evaluation is performed by calculating the cross-correlation coefficients between the impedance waveforms of PulmoVista 500 and the ventilator volume waveforms of OLV patients. The evaluation is carried out as in the primary analysis.
- In addition, a qualitative evaluation of the regional changes will be carried out. To do so, three blinded raters compare the corresponding sections of all OLV patients independently. Based on the information from the PulmoVista 500 video sequence provided, the raters evaluate which of the two halves of the lung is ventilated. The results are entered patient-related (pseudo-patient number) in the following table by the rater:

Pseudo-Patnr.	Valuation	
1	1	
2	2	
3	0	
4	1	
.	.	

Description of valuation:	0	not assessable
	1	right ventilated / left blocked
	2	left ventilated / right blocked

Tab. 1: Example of table for the qualitative evaluation of the OLV patients and the associated rating

The PulmoVista 500 video sequences to be assessed are created according to a workflow (see Appendix 7.3 Workflow for the creation of OLV videos) and made available to the raters. The pseudo-patient numbers are randomly generated by lot. These three tables of the raters will be merged into the KKS. A decision is considered positive or negative if at least two raters have come to the same result. In the opinion of one or more raters, is it not possible to judge the waveform (Code 0), the following assignment applies:

1x not evaluable & 2x same decision -> clear assignment in the table,
 1x not assessable & unequal decision of the remaining 2 raters -> drop out,
 2x or 3x not evaluable -> drop out.

A 2x2 Table will be created in the following form from the 3 tables of the raters (one of each rater):

Reference	Evaluation of the raters (with information provided by PulmoVista 500)	
	right ventilated / left blocked	left ventilated / right blocked
right ventilated / left blocked	a	b
left ventilated / right blocked	c	d

Tab. 2: Table for the accordance of rater and reality of the OLV patients

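### The first secondary (regional) endpoint is a cross-correlation of the global signal, but the OLV subgroup was sized and the regional conclusion written for a 2x2 comparison

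*Protocol*

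**What the plan says.** **Endpoint list.** The synopsis and Protocol 6.1.3 give: "First secondary endpoint: To assess the capability of PulmoVista 500 to detect changes in regional ventilation by evaluating the cross correlation" between the impedance waveforms and the ventilator volume curves during OLV. It is the only secondary endpoint given a rank.

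**Sample size.** Protocol 7.1 gives 22 evaluable and 25 enrolled OLV patients (two-sided 0.05, power 0.9) and states the target as a proportion: "With this sample size a difference of 0.1 of the proportion between reference and investigated variable shall be detected". No reference proportion is given.

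**Hypothesis.** For the secondary endpoint Protocol 7.2 says "it shall be tested, whether EIT can correctly differentiate between normal and single-lung ventilation". To reject the null, the regional information must match the clinical change, meaning that "EIT detects ventilation vs. no ventilation in each lung". The analysis is: "The diagnostic output of the EIT measurements will be compared with clinical ventilation settings in a 2x2 table". Correlation is not mentioned in that part.

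**SAP.** Sections 3.3.1 and 5.6.1 open with the OLV cross-correlation as the quantitative evidence that the device shows regional change. On method: "The evaluation is carried out as in the primary analysis". Under SAP 5.5 this means "a one sample t-test is performed to determine if the mean of the cross-correlation coefficients is significantly different from zero". SAP 5.6.1 then continues: "In addition, a qualitative evaluation of the regional changes will be carried out". Three blinded raters say which lung is ventilated, and the majority vote goes into a 2x2 table of right versus left. The outputs are a success rate, sensitivity and specificity with confidence intervals, without a null value or threshold.

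**Decision rule.** Protocol 7.3 says that no pass/fail criteria are defined.

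**The concern.** The endpoint that is ranked first is neither the one that was sized nor the one to which the regional conclusion is attached. This goes beyond wording, because the two analyses measure different things.

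Step 14 of the workflow in SAP 7.2 correlates the Global impedance column with ventilator volume. The export also holds local columns, but they are not used. Step 5 takes whole minutes before and after the intervention and leaves out the intervention itself. The correlation therefore shows that the total signal rises and falls with the breath. It cannot show which lung is being ventilated, because a global sum would track volume equally well if left and right were exchanged in the image. Only the 2x2 comparison uses regional information.

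At stake is what a reported success on the first secondary endpoint would mean. Protocol 3.2 says the data are needed for authorization in other countries. A regional claim resting on a significant global correlation would be open to immediate challenge.

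**Working it through.** **Inputs**
- n = 22, two-sided alpha 0.05, power 0.9, difference of 0.1 in a proportion, 15% drop-out: Protocol 7.1.
- SD 0.25: Protocol 7.1, given for the primary endpoint. Its use for OLV is an assumption.
- Test of the mean correlation against zero: SAP 5.5, carried over by SAP 5.6.1.
- Benchmark of 50% correct side with an exact two-sided 5% test: an assumption, since the documents give none.

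**1. What does n = 22 correspond to?**
- *As a proportion.* Take a reference near 1.0 (0.999) and a true value near 0.9. A single error then rejects, so power is 1 − 0.9^n. For n = 21 this is 0.891 and for n = 22 it is 0.902, so 22 is the smallest n that reaches 0.9.
- *As a correlation.* A difference of 0.1 at SD 0.25 gives d = 0.4, and the one-sample t-test needs 68 (power 0.902), which is the plan's own primary figure. A t-test would give 22 only if the SD were about 0.135 to 0.1375.
- *Drop-out.* 22/0.85 = 25.9, close to the stated 25.

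So 22 fits a proportion and does not fit the correlation at the stated SD. The reference near 1.0 is inferred. Other reference values give other sizes (0.8 versus 0.9 needs 137; 0.5 versus 0.6 needs 263).

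**2. OLV correlation against zero, n = 22**

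Noncentrality = (mean/0.25) × √22, critical t(21) = 2.080.

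| True mean correlation | Noncentrality | Power |
|---|---|---|
| 0.2 | 3.75 | 0.947 |
| 0.3 | 5.63 | 0.9997 |
| 0.8 | 15.0 | >0.999 |

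**3. Rater table against 50%, n = 22**

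16 of 22 correct gives p = 0.052 and 17 of 22 gives p = 0.017, so at least 17 are needed.

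| True side accuracy | P(at least 17 of 22) | Correlation significant, raters not above chance |
|---|---|---|
| 50% | 0.8% | 99% |
| 60% | 7% | 93% |
| 70% | 31% | 69% |
| 80% | 73% | 27% |
| 90% | 98% | 2% |
| 95% | 99.9% | <0.1% |

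The last column takes a mean correlation of 0.8 and independence of the two results. Because the correlation test then rejects almost surely, it is close to one minus the middle column.

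**4. Is the rater table the table in Protocol 7.2?** Not exactly. Protocol 7.2 asks about normal versus single-lung ventilation, and ventilation versus none in each lung. Table 2 of the SAP has only right-ventilated and left-ventilated, with no two-lung state. Blinded raters do not appear in the protocol, and Protocol 7.1 does not say which proportion it sized.

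**The case against.** - **Protocol 7.2 does give direction.** A reader might infer that nothing in the documents says which analysis carries the regional claim, so that the sponsor could claim success with raters at chance. The text does not support that. Protocol 7.2 requires the regional information to match the clinical change, and on that wording a significant correlation alone does not reject the regional null. Both results are also to be reported, so a poor rater result would be visible. What stands is that the endpoint list and the SAP are not aligned with Protocol 7.2.
- **The SAP does not reverse an order set in the protocol.** The secondary part of Protocol 7.2 contains no correlation, so it has no order to reverse. The conflict is with the endpoint definition.
- **Failing the rater table is undefined.** With no pass/fail criteria and only intervals planned, the 50% benchmark is this review's illustration. This is correct, and it means that the only OLV analysis with a formal test is the one without regional content.
- **The divergence may never arise.** If side accuracy is 90% or more, the two results conflict in about 2% of trials or fewer, and the reconstruction of n = 22 suggests that the planners expected accuracy in that region. This also stands. The rule matters for the case in which the device does less well.
- **The weak null is a separate matter.** Much of the contrast comes from testing a correlation against zero, which is an issue for the primary analysis too. But a stricter null would still leave the global signal without left/right information.

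**Conclusion.** The inconsistency is real and should be corrected. The synopsis, Protocol 6.1.3 and SAP 3.3.1 and 5.6.1 place the regional endpoint on a global correlation tested against zero. Protocol 7.1 and 7.2 place it on a proportion and a 2x2 comparison. Meeting the endpoint as listed would not show regional detection.

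That conclusion rests on the text and on the column used in the workflow, and needs no assumption. Its practical size does need assumptions: SD 0.25 for OLV, a 50% benchmark, an exact test, and independence of the two results. Under these the correlation test is nearly certain to be significant from a mean of 0.3 upward, while the rater table separates good from poor side identification. The two part company mainly below about 90% accuracy.

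**What to change.** 1. In the synopsis, Protocol 6.1.3 and SAP 3.3.1 and 5.6.1, make the 2x2 comparison of EIT output with the documented ventilation state the first secondary endpoint and the only basis for the regional claim. Report the blinded-rater success rate with a two-sided 95% confidence interval.
2. State the benchmark proportion used in the n = 22 calculation, and read the lower confidence limit against it. Check that it is attainable: 22 of 22 correct has an exact lower limit of 0.025^(1/22) = 0.846, so a benchmark of 0.9 could not be cleared with 22 patients.
3. Reconcile Protocol 7.2 with Table 2 of the SAP. Either reword the question and conclusion in 7.2 to side identification, or add the two-lung state to the rating. Protocol 6.4.2.2 already has both states recorded.
4. Keep the OLV correlation as a descriptive subgroup estimate of the primary endpoint, with no separate test and no regional conclusion.

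The cost is mainly wording, since both analyses are already planned and no new patients or recordings are needed. Adding the two-lung state would mean further video clips and rater time. The sponsor gives up the easier route to the regional claim.
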